### **5.3 Duration of Therapy**

In the absence of treatment delays due to adverse event(s), treatment may continue for until one of the following criteria applies:

- Disease progression,
- Intercurrent illness that prevents further administration of treatment,
- Unacceptable adverse event(s),
- Patient decides to withdraw from the study, or
- General or specific changes in the patient's condition render the patient unacceptable for further treatment in the judgment of the investigator.
- If a female patient gets pregnant during the study

Patients will be removed from study when any of the criteria listed above applies. The reason for study removal and the date the patient was removed must be documented in the Case Report Form.

### **5.4 Duration of Follow Up**

Patients will be followed for 180 days after removal from study or until death, whichever occurs first. Patients removed from study for unacceptable adverse events will be followed until resolution or stabilization of the adverse event.

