#### **Post-treatment Period:**

Patients with progression of disease (PD), unacceptable toxicity, or uncontrolled intercurrent illness will be taken off the trial. Other criteria for discontinuation will include: patient withdrawal of consent, noncompliance with study medication or visits, or any change that would render the patient ineligible for further treatment. In those cases, patients will be entered on the post-treatment period. The end of study visit should occur within 30 days of the last dose of the study drug. Patient medical histories, physical examinations and laboratory tests will be obtained. Tumor imaging if not done in the last 30 days, will be ordered at this time. The investigator or designee will obtain follow-up information on the patient at 180 days after the last dose of the study drug or until death (if before 180 days).

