### **1.2 Secondary Objectives**

- To characterize the safety and tolerability of vorinostat in this patient population.
- To assess the time to tumor response (TTR).
- To assess the response duration (RD).
- To evaluate progression free survival (PFS).
- To assess overall survival (OS).

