#### **10.2.2 Overall Survival (OS)**

OS is measured from the start of treatment until death from any cause. OS is subject to censoring.

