## 12.4 Analysis of Secondary Endpoints

There are 5 Secondary Objectives:

- 1) To characterize the safety and tolerability of vorinostat in this patient population
- 2) To assess the time to response (TTR)
- 3) To assess the response duration (RD)
- 4) To evaluate progression free survival (PFS)
- 5) To assess overall survival (OS)

Secondary Objective 1 concerns toxicity and adverse events, hence will involve categorical variables. They will be tabulated via frequency distributions, and also dichotomized to report the proportion (and percentage) of patients experiencing a specified level (e.g., Grade 3-4) of toxicity. Analysis of these proportions (i.e., rates) will include both point and 90% confidence interval (CI) estimates, with the CI estimates calculated via Wilson's method. The 90% confidence level is appropriate for either the Stage 1 sample size (n=12) or even the Stage 2 sample size (n=29) planned for this Phase II trial.

Secondary Objective 2 concerns TTR, which is a continuous variable not subject to censoring. It will be summarized descriptively, reporting N, median, mean, standard deviation (SD), standard error (SE), minimum, maximum, and 90% CI for the mean calculated from the SE and asymptotic Normal distribution theory.

Secondary Objectives 3-5 concern censored time-to-event (TTE) endpoints. Their distribution will be estimated using standard survival analysis techniques, and the Kaplan-Meier (K-M) method. From the K-M life tables, both point and 90% CI estimates of various statistics of interest can be calculated (e.g., median, 6-month event-free rate, 12-month event-free rate, etc.). Statistical graphs of each K-M curve (with 90% CI lines) will be generated for visual display of these censored TTE endpoints.

There are 7 Exploratory Objectives:

- 1) To assess the association between a metabolic response by PET/CT after one cycle of chemotherapy and subsequent best tumor response according to standard anatomic response evaluation criteria (RECIST).
- 2) To assess the association between a metabolic response by PET/CT after the first and second chemotherapy cycle and PFS.
- 3) Flow sort diploid, aneuploid, and tetraploid populations of tumor cells from FFPE tissue blocks from patients who benefited from SAHA therapy and from patients who did not demonstrate a durable benefit.

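### Follow-up stops 180 days after a patient leaves treatment, so overall survival beyond about 6 months is probably informatively censored and rests on few deaths

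*Combined protocol and SAP*

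**What the plan says.** - **End of follow-up.** Section 5.4: "Patients will be followed for 180 days after removal from study or until death, whichever occurs first". The Schema (Post-treatment Period) starts the clock elsewhere: the investigator is to obtain "follow-up information on the patient at 180 days after the last dose of the study drug or until death". The study calendar (section 9) ends at an off-study evaluation, and no section provides for later survival contact.
- **What starts the clock.** Section 5.3 lists progression first, then intercurrent illness, unacceptable adverse events, withdrawal, change in condition and pregnancy, and adds: "Patients will be removed from study when any of the criteria listed above applies". Under the Schema, patients with stable disease or a response may stay on drug while they benefit.
- **The endpoint.** Section 10.2.2: "OS is measured from the start of treatment until death from any cause. OS is subject to censoring". Nothing more is said about when OS is censored.
- **The analysis.** Section 12.4 uses standard Kaplan-Meier for response duration, progression-free survival and OS. Its examples of what may be reported are "e.g., median, 6-month event-free rate, 12-month event-free rate, etc", with 90% confidence intervals. No sensitivity analysis for dependent censoring is planned.

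**The concern.** Kaplan-Meier assumes that patients censored at a given time have the same future risk of death as those still followed. Under this rule, patients who progress early drop out of the risk set about six months later, while patients doing well on drug remain. As time passes, the risk set is made up increasingly of patients still on treatment or only recently off it. If death is more likely after progression, the curve flattens too early.

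Information is also lost. Section 2.1 calls the disease indolent, with 5-year survival as high as 50-90%, so many deaths would fall outside a 180-day window and never be recorded. At stake are the OS median and any rate beyond 12 months. In a single-arm trial a reader sees only the absolute figure, and no control arm shares the distortion.

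**Working it through.** **The plan's own figures.** The only design calculation is the Simon design in 12.1.1. It reproduces: at least 1/12, then at least 3/29, gives exact alpha 0.148, power 0.9005 and probability of early termination 0.540. It does not involve OS, and no event count or precision is stated for OS.

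**Step 1, when the rule can bite.** The 180 days start at removal or last dose, so essentially nobody is censored by the rule before day 180. The 6-month rate is unaffected. A patient removed at day 56 (week 8) stays at risk to day 56 + 180 = 236, and only days 236-365 are missing from the 12-month estimate.

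**Step 2, model.** Assumptions not in the documents: constant removal hazard λ = ln 2 / (median months on treatment), constant death hazard h on treatment, and constant death hazard μ = ln 2 / (median survival after removal). The window is w = 180/30.44 = 5.91 months. With k = λ + h − μ, the fractions of patients at month t are:
- on treatment: A = exp(−(λ+h)t)
- off treatment and alive: C = λ·exp(−μt)·[1 − exp(−kt)]/k
- off treatment, alive and still followed (t > w): B = λ·exp(−μt)·[exp(−k(t−w)) − exp(−kt)]/k

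True OS is A + C. Kaplan-Meier converges to exp(−∫g), where g = (hA + μB)/(A + B).

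**Step 3, one case by hand.** Medians 6 months on treatment and 12 months after, h = 0: λ = 0.1155, μ = k = 0.0578. At t = 24:
- A = 0.0625, C = 2 × 0.25 × 0.75 = 0.375, so true OS is 0.4375.
- B = 2 × 0.25 × (0.352 − 0.25) = 0.051.
- Still followed: 0.0625 + 0.051 = 0.113, which is 26% of those alive.
- Share on treatment: 0.0625/0.113 = 55% of those followed, but 0.0625/0.4375 = 14% of those alive.
- Hazard used by Kaplan-Meier: 0.0578 × 0.051/0.113 = 0.026 per month. True hazard: 0.0578 × 0.375/0.4375 = 0.050.

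Integrating g gives Kaplan-Meier 57.3% against a true 43.8%, and a median near 29 months against 21. Expected observed deaths are 29 × (1 − exp(−μw)) = 29 × 0.289 = 8.4.

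**Step 4, range.** Deaths assume a data cut 30-54 months after entry.

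| Medians on / after treatment (months) | h per month | True 24-month OS | Kaplan-Meier | Bias at 12 months | Bias at 24 months | Deaths seen of 29 |
|---|---|---|---|---|---|---|
| 6 / 12 | 0 | 43.8% | 57.3% | +3.3 | +13.5 | 8.3 |
| 6 / 12 | 0.01 | 39.2% | 49.3% | +2.6 | +10.1 | 9.9 |
| 6 / 12 | 0.03 | 31.9% | 36.8% | +1.4 | +4.9 | 12.6 |
| 9 / 18 | 0 | 63.6% | 75.7% | +2.2 | +12.1 | 5.6 |
| 9 / 18 | 0.01 | 55.7% | 63.8% | +1.6 | +8.1 | 8.2 |
| 9 / 18 | 0.03 | 43.7% | 45.6% | +0.4 | +1.9 | 12.2 |
| 12 / 24 | 0 | 75.0% | 84.6% | +1.6 | +9.6 | 4.0 |
| 12 / 24 | 0.01 | 64.7% | 70.4% | +1.0 | +5.7 | 7.6 |
| 12 / 24 | 0.03 | 49.3% | 49.0% | 0.0 | −0.3 | 12.5 |

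With follow-up continued to the same cut, 14 to 25 deaths would be seen.

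**Step 5, other hazard shapes (simulated, bias at 24 months).**
- Hazard rising after removal (Weibull shape 1.5-2): +13 to +40 points.
- Hazard falling: −0.4 to +3.6 (shape 0.7) or −6.8 to −0.1 (shape 0.5).
- Death risk unrelated to leaving treatment: within 0.3 points of zero.
- Hazard higher on treatment than off: 42.5% against a true 50.2%, so downward.

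**Step 6, n = 29.** In two simulated scenarios (medians 6/18 and 9/24 months, h = 0.005), 6 to 7 deaths were observed on average and the median was not reached in 53-55% of trials.

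**The case against.** The case for leaving the plan alone has substance. OS is one of five secondary objectives, with no hypothesis, comparator or decision rule, and the go/no-go depends on response alone. Of the OS statistics that 12.4 names, the 6-month rate is untouched. The 12-month bias is small beside sampling error: with 29 patients and true 12-month OS near 80%, the 90% interval is about ±1.645 × √(0.8 × 0.2/29) = ±12 points even with no censoring. The 24-month rate is not named. All of this stands, and it sets the severity.

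Three stronger readings are tempting, and the documents do not support them.
- A reader might infer that OS is certainly biased upward. The documents contain no hazards, and Step 5 shows that the bias can vanish or reverse. Removal also has causes other than progression.
- A reader might infer a 24-month bias of at least 10 points throughout. A range of that kind depends on assuming that nobody dies on treatment, yet 12.5.2 has categories for early death. With modest on-treatment mortality the bias shrinks toward zero.
- A reader might infer that an early progressor tells us nothing about 12-month OS. That patient remains at risk to about day 236, and a death before then counts.

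What survives is narrower. The median is among the named statistics, censoring time is tied to outcome, and most deaths may go unrecorded. The loss of deaths matters even where the bias is nil.

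**Conclusion.** The concern holds in limited form, as something that should be fixed because the fix is cheap. Beyond about 6 months, OS censoring is probably informative. The 6-month rate is sound and the 12-month rate is off by about 0 to +3 points. The 24-month rate is off by roughly 0 to +14 points under constant hazards, with nil, downward or larger upward bias under other patterns. About 4 to 13 deaths in 29 patients would be observed, so the median may be inflated or not estimable.

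The mechanism follows from sections 5.3, 5.4 and 12.4. The sizes rest wholly on assumed hazards. Upward bias is the expected direction if death risk is higher after progression and does not then fall steeply. Nothing here touches the response endpoint or the conclusion drawn from it.

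**What to change.** 1. In 5.4 and the Schema, continue vital-status follow-up by telephone or record check, where consent allows, for every treated patient to one common data cut-off. The 12 months after last accrual that 12.2 already allows would serve, so the final analysis need not wait.
2. In 10.2.2, state that OS is censored only at the date last known alive or at that cut-off.
3. Reconcile the start of the 180 days, which is removal from study in 5.4 and last dose in the Schema. The dates can differ by weeks, because 6.1 and 6.2.1 allow up to 21 days' delay before removal.
4. If patients cannot be recontacted, report OS to 6-12 months only and say why.

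The gain is real but bounded. That cut-off gives Stage 2 patients only 12 to 29 months of follow-up (12 months plus up to 17 months of accrual). With follow-up of 33-39 or 41-53 months for Stage 1 and 12-21 or 12-29 months for Stage 2 (fast or slow accrual), the Step 2 model with the Step 4 medians and hazards gives about 8 to 21 deaths, against 3 to 12 under the present rule. The remaining censoring at the cut-off would be administrative and unrelated to outcome.

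The cost is an amendment, consent wording and some site time for about 29 patients, with no added scans. Section 8 and Appendices D and I show that patients have already been treated, so those past 180 days may need recontact and consent.

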## **6. DOSING DELAYS/DOSE MODIFICATIONS**

### **6.1 Retreatment Criteria**

Prior to administration of each new cycle following cycle one, patients must have recovered the following organ function:

- absolute neutrophil count  $\geq 1.5 \times 10^9/L$
- platelets  $\geq 100 \times 10^9/L$
- creatinine  $\leq 1.5 \times$  upper limit of normal (ULN)
- other drug related toxicity must have recovered to  $\leq$  grade 1 (excluding alopecia, controllable hypertension, leukopenia and lymphopenia)
- total bilirubin WNL
- AST(SGOT)/ALT(SGPT)  $\leq 2.5 \times$  ULN

Patients not fulfilling these criteria should have treatment delayed by 1 week to allow for recovery of organ function. Patients who cannot be retreated within 3 weeks (21 days) of the end of the previous cycle should be removed from study, unless they are deriving benefit. In the later case, a discussion with the PI and/or CTEP senior investigator will ensue.

## 6.2 Dose Modification Guidelines

### 6.2.1 During the Course of a Cycle:

The dose of vorinostat will be held during the course of the cycle for one or more of the following events:

- Grade 4 neutropenia lasting > 7 days
- Grade 4 thrombocytopenia
- Any grade 4 non-hematological toxicity
- Grade 3 non-hematological toxicity that cannot be controlled with appropriate supportive care measures.

Treatment can be restarted with a reduction in dose (refer to [table 3](#)) once the toxicity resolves to severity of grade 1 or less. Inability to start the next cycle within 3 weeks (21 days) of the scheduled start due to toxicity will result in removal of the patient from the study, unless the patient is deriving benefit. In the later case, a discussion with the PI and/or CTEP senior investigator will ensue.

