Vorinostat will be withheld for any possible or probable drug related grade 3 to 4 adverse event. Patients will be allowed to have 2 dose reductions (from 300mg/day D1-7 to 300mg/day D1-5) due to grade 3 nausea, emesis or diarrhea (not controlled by appropriate supportive care measures); due to other drug-related grade 3/4 non-hematological toxicity; due to grade 3/4 neutropenia associated with fever and/or grade 4 neutropenia and/or grade 4 thrombocytopenia ([section 6](#)). In the event a patient is experiencing clinical benefit from vorinostat and requires further dose reduction, a discussion between CTEP and PI will ensue.

Patients who cannot be retreated within 3 weeks (21 days) of the end of the previous cycle should be removed from study, unless they are deriving benefit. In the later case, a discussion with the PI and/or CTEP senior investigator will also ensue.

Patients who experience either stable disease, complete response, or partial response by RECIST criteria will be allowed to continue on vorinostat as long as they are experiencing benefits without intolerable/life-threatening side effects.

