## 5. TREATMENT PLAN

### 5.1 Vorinostat Administration

Treatment will be administered on an outpatient basis. Reported adverse events and potential risks are described in [Section 7](#). Appropriate dose modifications for vorinostat are described in [Section 6](#). No investigational or commercial agents or therapies other than those described below may be administered with the intent to treat the patient's malignancy.

On Day 1 of the first cycle of vorinostat will be initiated on a continuous daily oral regimen at 400mg PO. The dose may be reduced for individual patients in subsequent cycles depending on toxicity (See [Section 6.2.2](#)). Each treatment cycle will consist of 28 days of therapy.

Vorinostat can be taken with food. Patients need to swallow each capsule whole with a full glass of water. Capsules should not be chewed or opened. If a capsule is broken and the powder of the capsules gets on skin, patients should be instructed to wash the exposed area with copious amounts of water and to inform investigator or nurse of the fact.

Patients are required to record their daily dose in a "pills diary". Missed/ skipped pills or vomited doses should not be re-taken. Patients should be instructed to record those pills as missed doses in the diary and to inform investigator or nurse if that happens.

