### 6.2.2 Dose Modification for Subsequent Cycles

Laboratory parameters should be obtained within 72 hours prior to initiation of the next cycle of therapy.

| Table 3- Dose Reduction for Toxicity (based on events from previous cycle)                                  |  |
|--|--|
| Toxicity  | Dose Reduction*,†  |
| Grade 3/4 Neutropenia associated with fever
and/or
Grade 4 neutropenia
and/or
Grade 4 thrombocytopenia | 1st occurrence:
Reduce by 100 mg/day – 300mg/day (D1-7)
2nd occurrence: 300mg/day (D1-5), with 2 days of rest
3rd occurrence: Off study     |
| Grade 3 nausea, emesis or diarrhea (not controlled by appropriate supportive care measures)                        | 1st occurrence:
Reduce dose by 100 mg/day- 300mg/day (D1-7)
2nd occurrence: 300mg/day (D1-5), with 2 days of rest
3rd occurrence: Off study |
| Other drug-related grade 3/4 non-hematological toxicity**  | 1st occurrence:
Reduce dose by 100 mg/day – 300mg/day (D1-7)
2nd occurrence: 300mg/day (D1-5), with 2 days                                     |

|  |                                      |
|--|--------------------------------------|
|  | of rest
3rd occurrence: Off study |
|--|--------------------------------------|

\* If a patient is experiencing benefits from vorinostat and needs further dose reduction, a discussion will occur between CTEP and the PI.

\*\* Since fatigue can be a symptom of underlying malignancy, dose reductions will only be done if fatigue can be attributed to vorinostat. No dose reductions will be done for alopecia.

† Note: “D1-7” means for 7 contiguous days in a week for ALL the weeks that the patient will be on treatment (i.e, 300mg/day everyday from D1-28, without any days of rest). “D1-5” means for 5 days out of 7 days (i.e., 5 days on treatment/ 2 days of rest in a week) for a cycle of 28 days.

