| 
a- Vorinostat: continuous oral dose 400mg/day (or other dosage if drug reduction required).
 
b- Days -21 to day -1: informed consent, physical examination and medical history; vital signs including weight and height; review of concurrent medication; ECG; collection of archival tumor tissue.
 
c- Days -14 to day -1: limited physical examination with vital signs (including weight); review of new events on history; review of medication; performance status; tumor measurement (by CT or MRI) and PET/CT (optional). Laboratory tests, pregnancy test (if appropriate) and urinalysis should be done within 7 days from first drug intake.
 
d- CBC with differential and platelets; PTT, PT and INR.
 
e- Study visits assessments to be done on weeks 2 and 4 (<math>\pm 1</math> day) for the first cycle, then for the second cycle on week 5 and 7, (<math>\pm 1</math> day); then from week 9 on, every four weeks (<math>\pm 1</math> day) thereafter.
 
f- Albumin, alkaline phosphatase, total bilirubin, bicarbonate, BUN, calcium, chloride, creatinine, glucose, LDH, phosphorus, potassium, total protein, AST, ALT, sodium, magnesium.
 
g- Serum pregnancy test (women of childbearing potential).
 
h- Off-study evaluation.
 
i- PET/CT to be done on days -14 to -1; D28<math>\pm 3</math> days and D56<math>\pm 3</math> days (optional).
 
j- Blood for correlative studies on days 1 (prior to first dose of vorinostat), 7 (+-1day) and 28 (+-1day)
 
k- A tumor biopsy will be done if the tumor can be easily accessed.
 
L – PET/CT scans are optional and will be performed based on the availability of funding
 
m- If no blood exists from a selected patient, or the blood was of poor quality, Karmanos study personnel will recontact the patient to obtain new informed consent and draw a new blood sample.
 
n- For patients that have been on study longer than 2 years, office visits can be done every 12 weeks (<math>\pm 7</math> days), with medical history, concurrent meds, physical exam, vital signs, weight, performance status, and adverse events evaluation done also at that time
 
o- For patients that have been on study longer than 2 years, hematology labs and serum chemistry can be done every 6 weeks (<math>\pm 7</math> days)
 
p- For patients that have been on study longer than 2 years, tumor measurements can be done every 24 weeks (<math>\pm 10</math> days)
 |                |  |  |  |                |  |  |  |                |  |  |  |  |  |

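### Section 6.2.1 lists an in-cycle neutropenia hold only for grade 4 beyond 7 days and none for febrile neutropenia; this is narrower than the Schema's hold, and scheduled counts can rarely show that duration

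*Combined protocol and SAP*

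**What the plan says.** The Schema (Treatment Period) states: "Vorinostat will be withheld for any possible or probable drug related grade 3 to 4 adverse event". It sets no duration condition and does not exempt haematological events.

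Section 5.1 tells sites: "Appropriate dose modifications for vorinostat are described in" Section 6. There, 6.2.1 lists four in-cycle holds. The only neutropenia item is "Grade 4 neutropenia lasting > 7 days". Grade 4 thrombocytopenia is on the same list with no duration condition.

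Table 3 in Section 6.2.2 sets the next cycle's dose. Its first row begins "Grade 3/4 Neutropenia associated with fever" and also covers grade 4 neutropenia of any duration.

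Counts are taken at weeks 2 and 4 in cycle 1 and weeks 5 and 7 in cycle 2 (±1 day), "then from week 9 on, every four weeks" (Section 9, footnote e). After 2 years on study they may be 6 weeks apart (footnote o). Two further checks act at the cycle boundary:

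- Section 6.2.2: "Laboratory parameters should be obtained within 72 hours prior to initiation of the next cycle of therapy".
- Section 6.1: "Prior to administration of each new cycle following cycle one, patients must have recovered the following organ function", with a neutrophil count of at least 1.5 × 10⁹/L on the list.

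**The concern.** This is about patient safety and consistent conduct across sites. Two mandatory rules cover the same event with different thresholds, and no clause ranks them. Section 5.1 makes Section 6 the likelier working rule, and it is the more permissive one. An event serious enough to reduce the next cycle's dose need not stop the drug in the current cycle. The threshold that does stop it rests on a duration that the visit schedule was not built to measure.

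**Working it through.** **Step 1. Set the rules side by side** (events judged possibly or probably related).

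| Event | Schema | 6.2.1, in-cycle | Table 3, next cycle |
|---|---|---|---|
| Grade 4 neutropenia, more than 7 days | hold | hold | reduce |
| Grade 4 neutropenia, 7 days or less | hold | not listed | reduce |
| Uncomplicated febrile neutropenia: grade 3, or grade 4 of 7 days or less | hold | not listed | reduce |
| Afebrile grade 3 neutropenia | hold | not listed | no action |
| Grade 4 thrombocytopenia | hold | hold | reduce |
| Grade 3 thrombocytopenia | hold | not listed | no action |

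A grade 4 infection, or a grade 3 infection not controlled by supportive care, would be held under the non-haematological bullets of 6.2.1. The febrile gap is therefore uncomplicated febrile neutropenia, which the adverse event list in Section 7.1 classes under blood disorders.

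**Step 2. Find the gap between scheduled counts.** The day within a named week is not given, so both ends were tried.

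- Week n as its first day: D8, D22, D29, D43, D57, D85.
- Week n as its last day: D14, D28, D35, D49, D63, D91.

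Either way, the two visit counts within cycle 1 or within cycle 2 are 14 days apart, or 12-16 with ±1 day at each visit. From week 9 they are 28 days apart (26-30), which is one visit per 28-day cycle. After 2 years they can be 42 ± 7 = 35-49 days apart, longer than a cycle. Footnote o does not say whether the 72-hour pre-cycle labs still apply then.

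Across the cycle 1-2 boundary, week 4 to week 5 is 7 days under either reading (29 − 22 = 7; 35 − 28 = 7), or 5-9 with windows.

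**Step 3. Ask whether a spell of more than 7 days can be shown.** A grade 4 spell of L consecutive days contains two counts g days apart only if L ≥ g + 1.

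- Smallest in-cycle gap, g = 12: L ≥ 13. Spells of 8-12 days can never be grade 4 at both visit counts of a cycle.
- Nominal gap, g = 14: L ≥ 15.

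For spells lying wholly inside a 28-day cycle there are 28 − L + 1 possible start days. The ranges cover both readings above and a mixed placement (week 2 and week 4 on the last day, later visits on the first).

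| L (days) | Start days | Both visit counts inside, cycles 1-2 | From cycle 3 |
|---|---|---|---|
| 8 | 21 | 0 | 0 |
| 10 | 19 | 0 | 0 |
| 14 | 15 | 0 | 0 |
| 16 | 13 | 1-2 | 0 |
| 21 | 8 | 1-7 | 0 |

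An 8-day spell is seen even once at 9-15 of 21 start days in cycles 1-2, and at 1-7 of 21 from cycle 3. Two grade 4 counts 14 days apart would still only imply continuous grade 4 between them.

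The pre-cycle labs add a count only at the end of a cycle. In cycle 2 they fall 11-13 days after week 7 (first-day reading) or 5-7 days after it (last-day reading). By then Section 6.1 decides whether the next cycle starts.

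**Step 4. Bound the exposure.** After a week-2 grade 4 count at nominal days:

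- First-day reading: D8 to the D22 count is 14 daily doses.
- Last-day reading: D14 to the pre-cycle labs on D26-28 is 12-14 daily doses.

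This assumes no recheck. Under the Schema, no dose follows once the event is judged related.

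**Step 5. Bound the number of patients.** The documents give no grade 3 or grade 4 neutropenia rate. Section 7.1 puts decreased neutrophil count, any grade, in the column for at most 20%: 0.20 × 29 = 5.8 patients at most, of whom grade 3-4 cases are only a part. Section 2.2 describes dose-limiting toxicity as mainly non-haematological.

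**The case against.** A reader might infer that the Schema and 6.2.1 give opposite orders. They do not. The 6.2.1 list does not say that only these events are held, and it never tells a site to keep dosing. A site that holds under the Schema satisfies both texts. The Schema's next sentence also refers to Section 6, although for dose reductions, which supports reading the Schema as a summary. What stands is that a site working from 6.2.1 alone has no instruction to hold.

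A reader might also take 12-14 further doses as the expected course. A mandatory hold that depends on duration cannot be applied without following the count, so some recheck is implied. Investigators may repeat counts or stop treatment for an unacceptable event (Section 5.3). Related expected grade 4 events need an expedited report within 10 calendar days, and the Protocol Chair must review adverse events promptly (Section 11). These make it unlikely that a grade 4 count goes unnoticed. None of them sets a date for a repeat count or requires an in-cycle hold.

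The schedule argument has limits. The week 4 and week 5 counts can span an 8-day spell across the cycle boundary. From cycle 3, the lack of a scheduled mid-cycle count is a separate limitation that rewording the bullet does not cure.

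Finally, it is tempting to conclude that the Schema should drop its hold for afebrile grade 3 neutropenia because Table 3 takes no action on it. That is a clinical choice, and the documents do not compel it.

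**Conclusion.** The point holds as an inconsistency with a safety gap, at minor severity. Section 6.2.1 omits two events for which Table 3 reduces the next cycle's dose: grade 4 neutropenia of 7 days or less, and uncomplicated febrile grade 3/4 neutropenia. Its duration condition cannot be shown by the visit counts within a cycle for spells of 8-12 days, and at nominal visit days needs at least 15 days in cycles 1-2.

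The schedule result assumes visits on the first or last day of the named week and counts only scheduled visits within a cycle. The dose figure is a worst case. Few patients are likely to be affected. The response endpoint and the two-stage decision rule are not touched. Section 8 already reports two partial responses, and the Schema describes scans as already obtained from all patients, so most early-cycle treatment may be past.

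**What to change.** In 6.2.1, replace the neutropenia bullet with: *Grade 4 neutropenia, or grade 3/4 neutropenia associated with fever.* This matches Table 3's neutropenia triggers, moves toward the Schema and removes the duration condition.

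If the sponsor keeps the 7-day clause, require a repeat CBC about 8 days after any grade 4 neutrophil count, and still add febrile neutropenia as an in-cycle hold.

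In the Schema, state which hold rule governs. The sponsor should then decide, on clinical grounds, whether afebrile grade 3 neutropenia is held in-cycle. The same mismatch exists for grade 3 thrombocytopenia and for grade 3 non-haematological toxicity controlled by supportive care, and it can be settled in the same sentence.

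The cost is two short text edits, or a calendar footnote and a bullet plus the Schema sentence, with a few more dose interruptions or an occasional extra blood count. For patients already past the early cycles the benefit is small.
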